### **Randomization**

Patients will be randomly assigned (1:1) to receive either EBD (EBD group) or EST (EST group) using a digital en-block randomization system (block size of four).

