#### **Detailed description**

**Study design:** Single centre, open-label, randomized trial to be done in Asian Institute of Gastroenterology, India

**Study population:** All eligible consecutive patients with CD who developed DE-nova or anastomotic strictures will be included.

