### **Sample size**

Based on previous retrospective study, symptomatic improvement with EST and EBD (9.5% and 33.5% respectively, the estimated sample size is total 90 (45 in each group) keeping type 1 error as 0.05 and power as 80%.

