**Study design**

**Study type:** Interventional (clinical trial)

**Estimated enrolment:** 100 patients

**Allocation:** Randomized

**Intervention model:** Parallel assignment

**Masking:** none (open label)

**Primary purpose:** Therapeutic

**Official title:** Randomized controlled trial comparing endoscopic balloon dilation versus endoscopic stricturotomy for short strictures ( $< 3$  cm) related to Crohn's disease (the BEST-CD trial)

**Estimated start date :** August - September 2022 (after ethical approval)

**Estimated recruitment completion:** July - August 2023

**Estimated study completion date:** July - August 2023

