## Perforation or Bleeding (per procedure): Balloon Dilation and Electroincision

## Inclusion Criteria:

Primary confirmed diagnosis of CD with obstructive symptoms

- 1) Gastro-duodenal and ileo-colonic strictures (both de novo and anastomotic strictures)

- 2) Short strictures (<3 cm)
- 3) Fibrotic or mixed stricture (predominantly fibrotic)
- 4) Strictures treated with either EST or EBD.

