**Exclusion Criteria:**

1. No established diagnosis of CD;
2. No endoscopic therapy; and
3. A combination therapy of EST and EBD at the onset
4. Small bowel CD related stricture requiring enteroscopy guided dilation
5. Predominantly ulcerated strictures (mixed or pure ulcerated strictures)
6. Long strictures (>3 cm)
7. Pediatric Patients (<18 years)
8. Pregnant or lactating mother
7. Not willing to participate

Studies on ESTST vs EBD CD related anastomotic strictures

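### A fixed block size of four, printed in a single-centre open-label protocol, could let staff who track allocations know about one in three in advance

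*Protocol*

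**What the plan says.** The protocol's Randomization section states: "Patients will be randomly assigned (1:1) to receive either EBD (EBD group) or EST (EST group"), carried out "using a digital en-block randomization system (block size of four"). One size is given. The protocol mentions no varying sizes, no stratification factor and no withholding of the size from recruiting staff.

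The Detailed description calls the study a "Single centre, open-label, randomized trial", and the Study design section gives masking as "none (open label"). The population is "All eligible consecutive patients with CD" who have de novo or anastomotic strictures.

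Two eligibility criteria bear on the point. The inclusion list admits "Fibrotic or mixed stricture (predominantly fibrotic"). The exclusion list removes "Predominantly ulcerated strictures (mixed or pure ulcerated strictures").

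The Sample size section plans 90 patients. The Data analysis timeline and the Study design section plan 100.

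**The concern.** Permuted blocks are safe only if the next assignment cannot be worked out. Here the protocol discloses the block size, both procedures are performed openly, and one centre without strata means one sequence to follow. A digital system can hide the list, but it cannot hide what earlier patients openly received.

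Consecutive enrolment narrows the room for steering without closing it, because the rule covers only eligible patients and eligibility needs a judgement. The word mixed appears in both the inclusion and the exclusion criterion, and the predominant component decides. Someone who knows the next arm could call a borderline stricture in or out without visibly breaking the consecutive rule.

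The setting gives this weight:

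- The primary outcome is freedom from obstructive symptoms over one year, reported by patients and assessed by staff who know the arm.
- The Brief Summary already describes stricturotomy as the better technique, so recruiters may hold a preference.
- The planned comparison of proportions is an unadjusted chi-square or Fisher's exact test.
- With 45 per arm, one patient is 1/45 = 2.2 percentage points of an arm's rate.

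Recorded stricture features could be adjusted for, but adjustment would not fully remove bias from selective entry.

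**Working it through.** **Inputs.** Block size 4 and ratio 1:1 (Randomization), so each block holds two of each arm. One centre and open label (Detailed description; Study design). N = 90 (Sample size) or 100 (Data analysis timeline; Study design). Assumed: one unstratified sequence, and an observer who knows the block size and sees all earlier trial allocations in order.

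**The plan's own figure.** The protocol gives no predictability figure. Its only calculated design figure is N = 90, from "symptomatic improvement with EST and EBD (9.5% and 33.5% respectively, the estimated sample size is total 90 (45 in each group"). With two-sided 0.05, 80% power, pooled variance and no continuity correction:

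n = [1.960·√(2·0.215·0.785) + 0.842·√(0.095·0.905 + 0.335·0.665)]² / 0.24² = (1.139 + 0.468)² / 0.0576 ≈ 44.8, so 45 per arm and 90 in total.

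This reproduces the plan. N is used below only as a count of allocations; whether those input rates are the right ones is a separate matter.

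**Certain allocations, fixed block of four.** There are 4!/(2!·2!) = 6 equally likely orders: AABB, ABAB, ABBA, BBAA, BABA, BAAB. An allocation is certain when only one arm remains in the block.

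| Position | P(certain) | P(best guess is right) |
|---|---|---|
| 1 | 0 | 1/2 |
| 2 | 0 | 2/3 |
| 3 | 1/3 (AABB, BBAA) | 1/3·1 + 2/3·1/2 = 2/3 |
| 4 | 1 | 1 |
| Sum | 4/3 | 17/6 |

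- Share certain in complete blocks: (4/3)/4 = 1/3.
- N = 90: 22 complete blocks and 2 further patients, so 22 × 4/3 + 0 = 29.3, or 32.6%.
- N = 100: 25 × 4/3 = 33.3, or 33.3%.
- Best-guess rate in complete blocks: (17/6)/4 = 17/24 = 70.8%.
- Best-guess rate at N = 90: (22 × 17/6 + 1/2 + 2/3)/90 = 63.5/90 = 70.6%, against 50% with no information.

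**Blocks of 4, 6 and 8 in random order.** Each size has probability 1/3, and the observer knows the set of sizes but not their order. After each allocation the observer updates the probabilities of the possible numbers (a, b) left in the current block. The chance that the next is A is Σ P(a, b)·a/(a + b).

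The first block shows the effect. After AA, a fixed block of four makes the next B for certain. With mixed sizes, AA has probability 1/6, 1/5 and 3/14 in blocks of 4, 6 and 8, and the next is then B with probability 1, 3/4 and 2/3:

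P(B | AA) = (1/6·1 + 1/5·3/4 + 3/14·2/3) / (1/6 + 1/5 + 3/14) = 0.4595/0.5810 = 79%.

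Results for whole sequences, with 5,000 simulated for the mixed scheme:

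| Scheme | Certain, N = 90 | Certain, N = 100 | Best guess |
|---|---|---|---|
| Fixed 4 | 29.3 (32.6%) | 33.3 (33.3%) | 70.6% at 90, 70.8% at 100 |
| Random 4/6/8 | 2.02 (2.2%) | 2.29 (2.3%) | 67.9% |

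Under the mixed scheme the final arm sizes differed by 2 at the 95th percentile and by 4 at most, at both values of N. Under fixed blocks of four the difference is at most 2 at N = 90 and 0 at N = 100.

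**Other options.** The certain share is 1/4 for fixed blocks of 6 and 1/5 for fixed blocks of 8. For random 4/6 it is about 5% at N = 100, with a best guess of about 69%.

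**The case against.** Permuted blocks of four are a recognised method, and nothing else in the protocol conflicts with them. The figures measure predictability, not bias in the primary outcome. For harm to follow, staff must know the size, track every allocation, meet a borderline stricture at a predictable position, and change the eligibility call. Tracking may also be harder than it looks: the Study settings section reports more than 200 dilation or stricturotomy procedures a year against 100 planned trial patients, so trial procedures must be told apart from the rest.

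The remedy is also partial. The best-guess excess over chance falls from 70.8 − 50 = 20.8 points to 67.9 − 50 = 17.9, a relative reduction of 2.9/20.8 = 14%. If staff act on likely guesses as well as on certain ones, most of the exposure remains. Who holds the list and when an allocation is released may be set out in a document that is not shown.

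Much of this stands as a limit on size. One in three is the figure for a fully informed observer, and no steering is shown. It does not remove the point. The protocol itself fixes and prints the single block size, and no other document can undo that disclosure. Certain foreknowledge is the form easiest to act on, and it can be almost eliminated at little cost.

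**Conclusion.** The concern holds. Followed exactly, the plan leaves one third of allocations in complete blocks deducible with certainty: 29.3 of 90 or 33.3 of 100. This rests on one unstratified sequence and on staff who know the size and see all earlier trial allocations. If the list were in fact stratified, tracking would have to be done within each stratum, and further incomplete blocks would lower the share somewhat. The size of any bias in the primary outcome cannot be derived from the protocol. This is a change that should be made because it is cheap and protects the main safeguard of an unmasked trial. It is not evidence that allocation has been or will be steered.

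**What to change.** 1. Generate the sequence with randomly varying block sizes, for example 4, 6 and 8.
2. Remove the sizes from the protocol that recruiting staff see, and hold them in a restricted randomisation document.
3. State in the protocol that each allocation is released only after eligibility, including the fibrotic or ulcerated call, has been recorded and the patient registered. If the system already works this way, one sentence saying so is enough.

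Before enrolment this costs a new list and one or two protocol sentences. If the digital system cannot vary block sizes, someone outside recruitment can generate the list and load it. The downside is the slightly larger possible arm-size difference shown above. The Study design section estimates a start in August to September 2022. If recruitment has begun, the change can cover only the remaining patients, and the report should describe both methods.

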## **Study description**

### **Brief Summary**

Crohn’s disease (CD) related strictures can be treated endoscopically by endoscopic balloon dilation (EBD) or endoscopic stricturotomy (EST). EBD is the established endoscopic treatment for short strictures in Crohn's disease. However, roughly half had recurrent symptoms and two third require surgery after EBD. ES have been used initially for endoscopic treatment of patients for whom EBD was unsuccessful. Subsequently it was shown that ES is a better modality for treating CD related strictures (specially short and anastomotic strictures) than EBD lowering the risk of future surgery and procedure related perforation albeit with an increased risk of bleeding. ES was shown to be non-inferior to re-do surgery in chronic pouch anastomotic sinus in ulcerative colitis (UC) and ileocolic anastomotic strictures in CD thus reducing surgical morbidity. However, these two modalities have not been compared in a randomized controlled manner. We aimed to compare the two endoscopic treatments with regard to clinical success, need for surgery or additional endoscopic procedure and safe-

ty in patients with CD who have short (<3 cm), predominantly fibrotic stenosis excluding those in the small bowel not accessible by endoscope/colonoscopy.

Condition or disease	Intervention or treatment
Crohn's disease	Intervention: Endoscopic balloon dilation
	Intervention: Endoscopic stricturotomy

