#### **Study settings:**

The proposed study would be conducted in a high volume tertiary GI centre (Asian Institute of Gastroenterology) performing nearly more than 200 EBD/ES procedures per year with an well established inflammatory bowel disease (IBD) registry with more than 7000 IBD patients under follow up.

The study will be conducted after approval by the institutional ethics committee. Written informed consent would be taken from each participants and the study would conform to the 1975 Declaration of Helsinki ethical guidelines.

**Data collection:** A survey administration software (google forms) would be used to collect the participant data (age, sex, ethnicity, clinical features, smoking status, details of CD diagnosis, disease phenotype, extra intestinal manifestations, family history, history of intestinal resection, details of stricture diagnosis, details of stricture: degree, number, location, radiological finding: concurrent abscess, fistula, enhancement;

drug history for CD, procedural details: technical success, symptomatic improvement, endoscopic improvement, stricture related emergency visit or hospitalization, complications, subsequent need for additional endoscopic procedures or surgery upto a follow up of 1 year). Follow-up details would be collected via physical visit or telephonic communication.

**Technique and instruments:** EBD procedures will be performed with wire guided CRE pneumatic balloon (controlled radial expansion balloon, Boston scientific, Marlborough, MA, USA) of various sizes based on tightness of the stricture (10-12 mm, 12-15 mm, 15-18 mm, 18-20 mm) with graded dilation with inflation pressures varying from 3-8 ATM pressure. Balloon was inflated for at least 2 minutes and slowly deflated. For mild ooze post EBD, balloon tamponade will also be done with the same balloon. A maximum of two sessions of dilation will be allowed with a minimum interval of 15-30 days between them. Additional EBD sessions would be considered as additional endoscopic procedure for the purpose of the study.

Endoscopic stricturotomy would be done using a needle knife/insulted tip (IT) knife with the following electrocautery settings : Endocut Q (effect 3, cut duration 1, cut interval 3) as per by global IIBD group consensus.

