### **Data analysis**

Statistical analysis: Statistical analysis would be done by using statistical package for social sciences (SPSS, IBM, NY, USA). Chi-square/Fisher's exact test was used to

compare categorical variables and Mann-Whitney test would be used to compare continuous variables between the two groups. P-value  $<0.05$  would be considered statistically significant

**Timeline:** 2 years

Recruitment of 100 CD patients with stenosis requiring EBD or EST over 1 years: follow up over 1 year.

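### A fixed, stated block size of four without stratification, in a single-centre open-label trial, makes allocation partly predictable and leaves stricture type to chance

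*Protocol*

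**What the plan says.** - **Allocation.** The Randomization section sets a 1:1 ratio between the two arms, with the list produced "using a digital en-block randomization system (block size of four". It names no stratification factor and does not say that block sizes vary or are withheld from recruiters.
- **Setting.** The Detailed description calls this a "Single centre, open-label, randomized trial" and plans to include all eligible patients consecutively. Study design gives masking as "none (open label".
- **Population.** The Inclusion Criteria admit "Gastro-duodenal and ileo-colonic strictures (both de novo and anastomotic strictures". Entry also requires a judgement that the stricture is mainly fibrotic, and the Exclusion Criteria require one that it is not mainly ulcerated.
- **Stricture type.** The Brief Summary reports stricturotomy as better than dilation, "specially short and anastomotic strictures". All enrolled strictures are short, so anastomotic type is the part of that statement that still varies between patients.
- **Baseline data.** Study settings lists "details of stricture: degree, number, location" and history of intestinal resection. No field is named de novo or anastomotic. The literature table under Eligibility criteria does enter anastomotic as a location, so type should be derivable before randomisation.
- **Analysis.** Data analysis covers categorical variables in one sentence, which begins "Chi-square/Fisher's exact test was used to". It mentions no stratum or covariate.
- **Primary outcome.** Outcome measures defines it as freedom from obstructive symptoms over one year.

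**The concern.** There are two weaknesses in how the list is built.

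1. **Predictability.** In an open-label trial at one centre, staff see each allocation as it is made. If they also know that every block holds two of each treatment, the end of each block can be deduced, even if the list itself is hidden. Because eligibility turns on judgement, foreseeable allocation gives a route for easier strictures to reach one arm. The outcome is symptoms assessed without masking, and no later analysis fully repairs selection at entry.

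2. **Chance imbalance.** The protocol singles out anastomotic strictures as a group in which stricturotomy does better, and it collects the data to identify them. An unstratified list of 90 to 100 patients can still leave the arms noticeably different on this factor.

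**Working it through.** **Plan's own figure.** Sample size gives 90 in total for 9.5% v 33.5%, type 1 error 0.05 and power 80%. With the pooled two-sided formula and no continuity correction, the mean rate is 0.215:

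n per arm = [1.96 × √(2 × 0.215 × 0.785) + 0.8416 × √(0.335 × 0.665 + 0.095 × 0.905)]² / 0.24² = (1.1387 + 0.4676)² / 0.0576 = 44.8, so 45 per arm and 90 in total.

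The figure reproduces, with power 80.2%. The 24-point difference serves below only as a yardstick. Whether those two rates belong to the primary outcome is a separate question.

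**Predictability of fixed blocks of four (block size from Randomization).** Assume a recruiter who knows the block size and every earlier allocation.

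- The fourth assignment is always determined. The third is determined when the first two match, with probability 1/3. Share known in advance = (1 + 1/3)/4 = 33.3%.
- For 90 patients (22 full blocks and two further patients) this is 22 × 4/3 = 29.3 assignments. For 100 patients (25 blocks) it is 33.3.
- The chance of a correct best guess by position is 1/2, 2/3, (2/3 × 1/2 + 1/3 × 1) = 2/3, and 1. The mean is 2.833/4 = 70.8%, against 50% with no information.

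**Imbalance in stricture type without stratification.** The anastomotic share q is not in the protocol, so it is taken as 30% to 50%. With n = 45 per arm, the SD of the between-arm difference is √(2q(1 − q)/n).

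| q | SD | P(≥10 points) | P(≥20 points) |
|---|---|---|---|
| 30% | √(0.42/45) = 9.7 points | about 30% | about 4% |
| 50% | √(0.50/45) = 10.5 points | about 34% | about 6% |

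A simulation of 90 patients with actual blocks of four (4,000 runs per scenario) agrees: 29-31% and 34-35% for 10 points or more, and 3-5% and 5-6% for 20 points or more. Blocks of four within stricture type bring all of these to about 0%.

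**Possible shift in the crude estimate.** This needs stricture type to be prognostic. The protocol gives no figure, so a 20- to 30-point difference in one-year success is assumed.

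- A 10-point imbalance shifts the estimate by 0.10 × 20 = 2 to 0.10 × 30 = 3 points.
- A 20-point imbalance shifts it by 4 to 6 points.
- The planned difference is 33.5 − 9.5 = 24 points.

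**Validity and power, from the same simulation.**

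- Type I error lies between 4.4% and 5.8% in every setting. For the crude chi-square with plain blocks it is 5.3% to 5.8%. The simulation error is about 0.3 points.
- With an assumed 20-point prognostic difference in the dilation arm, plain blocks with crude chi-square give power of 79.6% (q = 30%) and 82.7% (q = 50%). Stratified blocks with Cochran-Mantel-Haenszel give 80.4% and 83.4%. The gain of under 1 point is within simulation error (√(0.8 × 0.2/4000) = 0.6 points per estimate).

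**The case against.** The strongest reply is that nothing here is an error. Chi-square after unstratified blocked randomisation is a valid test, chance imbalance is already reflected in its p-value, and adjustment gains almost no power. All of this stands. A reader might infer that the stated test is wrong, or that the trial has no adjusted analysis. The documents support neither. The Data analysis sentence is generic, does not single out the primary outcome, and an adjusted analysis could sit in a statistical analysis plan that is not shown.

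A reader might also infer that imbalance is likely and will bias the result. That goes too far as well. An imbalance of 10 points or more has roughly a one-in-three chance, and one of 20 points is uncommon. The Brief Summary describes a larger treatment benefit in anastomotic strictures, which is effect modification. It does not say that type predicts outcome regardless of treatment, so the 2- to 6-point shift rests wholly on an assumed prognostic difference.

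On predictability, the 33% and 71% are worst-case figures for a recruiter who keeps count. Consecutive enrolment restricts selective entry, and nothing says that recruiters see the list in the digital system. These points reduce the risk without removing it: the trial is unmasked, earlier allocations are visible at a single centre, the block size is printed in the protocol, and eligibility needs judgement.

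**Conclusion.** The point holds as a weakness of the randomisation scheme that is cheap to remove. It is not an error in a figure or a fault in the test.

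- **Predictability is the firmer part.** Up to one third of assignments can be known in advance and about 71% guessed. This rests only on the stated block size and on a recruiter who tracks allocations. It does not show that anyone would steer patients.
- **Chance imbalance is secondary.** It rests on an assumed 30-50% anastomotic share. Its effect on the estimate also needs an unsupported assumption about prognosis.
- **Stratifying does not cure dilution.** If 30% are anastomotic and the assumed event rates under stricturotomy are 15.5% (de novo) and 3.5% (anastomotic), against 33.5% with dilation, simulated power is about 70-72% with or without stratification. This is why the effect should also be reported by type.

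**What to change.** **In Randomization:**

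1. Use randomly varying block sizes, and keep them out of any document that recruiting endoscopists see. This lowers predictability but does not abolish it in an open-label trial.
2. Stratify the list by stricture type, de novo v anastomotic. Class each patient before randomisation from the recorded location and resection history. Past resection alone does not place the treated stricture at the anastomosis, so add an explicit field and a stated rule for patients with both types.

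**In Data analysis, if the list is stratified:** analyse the primary outcome by the same factor, with a Cochran-Mantel-Haenszel test and a Mantel-Haenszel risk difference with 95% CI. Report the effect by type, because the pooled estimate cannot show whether it differs. Keep the crude chi-square as a sensitivity analysis.

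**Cost:** a slightly more complex list set-up, one baseline field and a few sentences. The sample size stays at 90. Incomplete final blocks in two strata can leave the arms slightly unequal, by at most half the largest block size per stratum (with blocks of four, 2 + 2 = 4 patients). If recruitment has already finished, the list cannot be changed, but the stratified analysis can still be fixed before the outcome data are analysed.
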